1.0 BACKGROUND AND RATIONALE

1.1 Disease Background

Stroke is the leading cause of adult-onset of disability. Recent studies estimate that stroke affects about 795,000 people in the U.S. each year, resulting in a prevalence of over 6.4 million individuals^{1,2}. A large proportion of these stroke survivors (up to 80%) experience considerable gait deficits, including reduced walking speeds and asymmetrical walking patterns, limiting their capacity for community ambulation³. These mobility deficits are due to a combination of numerous neuromuscular changes following the stroke including: reduced corticospinal drive and control, muscle atrophy and weakness, impaired balance and posture control, abnormal muscle synergies, and visuo-cognitive deficits.

The goal of post-stroke rehabilitation is to reintegrate individuals back to their highest level of function for employment, social and community participation⁴. The return of mobility and walking is a crucial part of this return to function⁵. Gait training has been a major focus of stroke rehabilitation⁴, with self-selected walking speed considered to be one of the most important measures of stroke rehabilitation. It is thought to be a predictor of health status, community mobility, social interaction, and overall quality of life. Stroke survivors are currently classified based on their self-selected walking speeds as: non-ambulators (unable to walk), limited household ambulators (<0.4m/s), limited community ambulators (0.4-0.8m/s), and community ambulators (>0.8m/s)⁶. These walking speeds are however significantly lower than those exhibited by healthy controls (1.3-1.5 m/s)⁷.

Physical rehabilitation has many methodological approaches to training post stroke. The 2 most commonly applied techniques are task specific training, in this case gait training and impairment based training, which is more focused on balance, and functional deficits. The use of unconstrained robotic exoskeletons may allow gait retraining to be integrated with activities of daily living. However, there are very few studies that looked at the impact of a robotic exoskeleton on walking performance in the mild-moderate-stroke population^{8,9}. This study will compare task specific training using a robotic exoskeleton SMA vs. IPT impairment based physical therapy in the outpatient setting for individuals post-stroke.

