2.0 STUDY OBJECTIVES

2.1 Primary Objectives

- 2.1.1 To determine the effect on gait speed, as assessed by the 10 meter walk test of the SMA device vs. traditional physical therapy care in an outpatient setting for post stroke individuals.

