2.3 Endpoints

The outcome measures will be assessed prior to the start of Outpatient Therapy, after 9 Outpatient PT visits , after 18 sessions and a 3 month follow up testing visit, which will be the endpoints of the study;

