2. **10 Meter Walk Test:** The 10mWT assesses walking speed in meters per second over a short duration. Changes in gait speed that result in a transition to a higher category of ambulation classification resulted in better function and quality of life¹⁵. In the 10mWT, subjects are directed to walk at their self-selected and maximum safe speed with the effects of acceleration and deceleration minimized (by adding 1 meter at the beginning and at the end of the course to isolate the subject's steady state speed). Any assistive device and orthotic should be kept consistent and documented. It should also be documented whether the gait is tested at "preferred walking speed" or "fastest walking speed". The 10mWT has been validated for the stroke population and is accepted as a responsive, functional measurement of the patient's ability to ambulate over short distances such as those typical to a household setting. A small meaningful change for people with stroke is 0.06 meters/second; a substantial meaningful change is 0.14 meters/second¹⁴. A speed of <0.4 and >.08 m/s is an exclusion in the study.
3. **Berg Balance Scale (BBS):** The BBS is a 14-item objective measure designed to assess static balance and fall risk in adult populations and is a well-accepted measure in the stroke literature. The functional activities that are assessed include sitting and standing balance during transfers, altered base of support, reaching, turning, eyes open and closed. Each item is scored from 0 to 4 points. The maximum score is 56 points. A score from 0 to 20 represents balance impairment, 21 to 40 represents acceptable balance, and 41-56 represents good balance. The minimal detectable change score for individuals with acute stroke is 6.9 points¹⁶ and 4.66 points in chronic stroke¹⁷.
4. **5 Times Sit to Stand Test (5xSST):** The 5xSST is used to measure functional lower extremity strength during the transitional movement of sit to stand. The individual is timed in moving from the start position of sitting, arms across chest, in a standard chair without armrests to fully standing five times. The minimal detectable change in individuals with chronic stroke is 3.6 seconds.¹⁸
5. **Gait Analysis:** A quantitative means of assessing gait function in adults post-stroke based on spatiotemporal parameters of gait. The GaitRite® system is an electronic walkway with integrated sensors and is considered a reliable and valid means of assessing gait changes poststroke.

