8.3 Data Analyses Plans

The outcome measures for each subject (listed in Section 5.2) are recorded during 0th, 10th and 18th session of the training cycle and at 3 month follow up visit. Photographs and video without individual subject's faces will be recorded as this device is not commercially available yet and dissemination of accurate information will be assisted by showing how the device operates when donned and used by subjects. Outcome measures are compared with in the subject and across the subject pools for statistical significant differences using Multiple ANOVAs. All the statistics will be performed at 90% confidence level.

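### Section 8.3 tests every outcome at alpha 0.10 without giving a reason, and the plan never names the 10mWT speed, visit or ANOVA effect that decides the primary objective

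*Combined protocol and SAP*

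**What the plan says.** Section 2.1 gives the primary objective: "To determine the effect on gait speed, as assessed by the 10 meter walk test of the SMA device vs. traditional physical therapy care". It names no speed condition, visit or contrast.

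Section 8.3 is the whole analysis plan: "Outcome measures are compared with in the subject and across the subject pools for statistical significant differences using Multiple ANOVAs", followed by "All the statistics will be performed at 90% confidence level". The synopsis adds only that multiple ANOVAs will be used. Neither place orders or gates the tests, corrects for multiplicity, or treats the primary objective separately.

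On the speed, the 10mWT description in 5.2 says that "subjects are directed to walk at their self-selected and maximum safe speed", and then "It should also be documented whether the gait is tested at 'preferred walking speed' or 'fastest walking speed". The first sentence reads as two speeds; the second could mean that only one is tested. Section 1.1 calls "self-selected walking speed considered to be one of the most important measures of stroke rehabilitation" and defines the 0.4-0.8 m/s ambulation class by it, and 3.1 uses the same band for entry.

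On the visit, 2.3 lists baseline, the assessment after 9 visits, and then "after 18 sessions and a 3 month follow up testing visit, which will be the endpoints of the study".

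**The concern.** Three choices decide the primary result, and all three are open: the speed, the visit and the effect. On the effect, 8.3 gives within-subject and between-group comparisons equal standing. Within-subject change does not compare the arms, so a significant improvement over time in the SMA arm would not answer 2.1. Among effects that do compare the arms, 8.3 does not choose between the group effect, the group-by-time interaction and the difference at one visit.

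Two analysts who both follow 8.3 could therefore reach different primary conclusions from the same data, and the choice could be made after the results are seen. That cannot be repaired credibly after analysis. The 90% level adds to the problem, because each candidate test already carries a 10% false-positive risk.

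**Working it through.** **Inputs from the documents.** Confidence level 90% (8.3); two possible speeds (5.2); 80 subjects, 40 per arm, 30% attrition (5.1), so 40 × 0.70 = 28 completers per arm; meaningful changes of 0.06 and 0.14 m/s (5.2: "A small meaningful change for people with stroke is 0.06 meters/second; a substantial meaningful change is 0.14 meters/second").

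**Assumptions, because the documents give no figure.** Correlation between the tests of the two speeds 0.7-0.9; between visits 0.5-0.8; SD of speed 0.15, 0.20 or 0.25 m/s; baseline-to-post correlation 0.5, 0.7 or 0.8; two-sided tests.

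**1. One test.** Alpha = 1 − 0.90 = 0.10, critical value 1.645. For a single two-sided contrast this is 5% in each direction. For the group-by-time F test it is 10% with no direction, because that test has (2 − 1)(4 − 1) = 3 numerator degrees of freedom with four assessments, or 2 with three.

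**2. Either of two speeds may count, one contrast each.** Risk = 1 − P(|Z1| < 1.645 and |Z2| < 1.645), bivariate normal:

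| Correlation | Risk at alpha 0.10 | Risk at alpha 0.05 |
|---|---|---|
| 0.9 | 13.6% | 7.0% |
| 0.8 | 15.0% | 7.8% |
| 0.7 | 16.1% | 8.3% |

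Outside this range, at alpha 0.10, the risk is 12.6% at a correlation of 0.95, 17.6% at 0.5 and 19.0% at 0. A simulation with one group-by-time ANOVA on each speed at alpha 0.10 gives the same 14-16%. Changing alpha alone therefore does not restore 5% if two speeds can count, and naming the comparison alone leaves 10%.

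**3. Visits tested separately, any one result counting, alpha 0.10.** One speed at three post-baseline visits: 18-24%. Two speeds at three visits: 25-36%. These figures apply only under that rule.

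**4. Power cost of 0.05.** Unadjusted t-test, 28 per arm, noncentral t. The difference detectable with 80% power rises from 0.67 to 0.76 SD. Power for 0.14 m/s:

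| Assumed SD (m/s) | Alpha 0.10 | Alpha 0.05 |
|---|---|---|
| 0.15 | 96% | 93% |
| 0.20 | 83% | 73% |
| 0.25 | 66% | 54% |

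At SD 0.20 the detectable difference moves from 0.135 to 0.152 m/s, and so crosses 0.14.

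**5. What ANCOVA recovers.** Detectable difference at 28 per arm: change score = d√(2(1 − r)); ANCOVA = d√(1 − r²), with d = 0.673 at 0.10 and 0.762 at 0.05.

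| r | Change score, 0.10 | Change score, 0.05 | ANCOVA, 0.05 | Share of the rise recovered |
|---|---|---|---|---|
| 0.5 | 0.673 | 0.762 | 0.660 | all |
| 0.7 | 0.521 | 0.591 | 0.545 | (0.591 − 0.545)/(0.591 − 0.521), about two thirds |
| 0.8 | 0.426 | 0.482 | 0.457 | (0.482 − 0.457)/(0.482 − 0.426), under half |

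ANCOVA can equally be used at 0.10, so its gain does not cancel the cost of changing alpha.

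**The case against.** The strongest reply is that 0.10 is a disclosed choice. No section claims a 5% error rate or a regulatory purpose, and this is a single-site study of 80 subjects. That stands: the level contradicts nothing in the documents and is not a calculation error. What is missing is a reason for it.

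A second reply is that the context points to self-selected speed. Sections 1.1 and 3.1 do lean that way, but background text and an entry band do not define an endpoint.

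Three stronger readings are tempting and are not supported:

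- A reader might infer that the primary error rate is 25-36%, or even 1 − 0.9⁶ = 47% with six independent tests. Those figures need separate visit tests with any one success sufficing, and the plan does not state that rule. A repeated-measures ANOVA would test the visits jointly. Other rules, equally unstated, would keep the risk at or below 10%: requiring both speeds (4-6%), or gating visit tests behind the group-by-time test (8-9%).
- A reader might infer that half of the false positives favour SMA whatever the analysis. That holds only for a single contrast.
- A reader might infer that baseline adjustment makes the move to 0.05 free. Steps 4 and 5 of the working show that it does not.

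**Conclusion.** The point holds in two parts of different strength.

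**The primary comparison is not named.** This is certain from the text and must be fixed, because speed, visit and effect could all be chosen after the results are known.

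**Alpha 0.10 is unexplained.** The 10% risk for one test follows directly from 8.3. The 5% in each direction additionally needs a single two-sided contrast, and 8.3 does not state sidedness. Moving to 0.05 is a recommendation to adopt or answer with a justification.

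The 14-16% figure rests on assumed correlations and on either speed being allowed to count. It shows what the silence permits and is not an error rate that the plan commits to. The plan gives no power or target effect, so the power cost of 0.05 breaches no stated figure.

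**What to change.** In 2.3 and 8.3, name one primary comparison before the data are analysed. Possible wording: *The primary comparison is the between-group difference in self-selected 10mWT speed at Post Testing (after Session 18), estimated by ANCOVA with baseline self-selected speed as covariate, in all randomised subjects by assigned group, tested once at two-sided alpha 0.05 with a 95% CI.* State how missing Post Testing values will be handled, since 30% attrition is planned.

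Self-selected speed is suggested because 1.1 and 3.1 lean towards it, and Post Testing because every description of the schedule includes it. Another speed or visit would serve if fixed in advance.

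Make the other speed, the other visits and the other 5.2 measures secondary. Report them as estimates with confidence intervals, or test them with a Holm correction. Remove the blanket 90% rule; if 0.10 is kept for the primary test, 8.3 should give the reason and state the 10% risk.

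The cost is wording, plus the loss of power shown above if alpha moves to 0.05.

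Separately, 4.3 says there is no follow-up after the post-treatment testing, while 2.3, 5.2, 5.3 and 8.3 include a follow-up assessment (at 3 months in 2.3, 5.2 and 8.3). These sections must be reconciled.

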9.0 STUDY MANAGEMENT

9.1 Data Management and Monitoring/Auditing

Subjects' records will be kept completely confidential. Data will be collected and kept confidential and compliant with HIPPA requirements. Research data will be de-identified and stored in locked cabinets in the lab with access only to research staff. Electronic data will be de-identified and kept on secure, password protected files and password protected computers.

9.2 Record Retention

Study documentation will be collected and kept confidential and compliant with HIPPA requirements. Photographs and video without recording individual subject's faces will be recorded as this device is not commercially available yet and dissemination of accurate information will be assisted by showing how the device operates when donned and used by subjects. Data will be held for 3 years after the study is completed and published.

